8.5.10.5. Follow-Up of Adverse Events

The Investigator must continue to follow all SAEs and non-serious AEs considered to be at least possibly related to ATYR1940 either until resolution or the Investigator assesses them as chronic or stable. This follow-up may extend after the end of the study.

8.5.10.6. Reporting Safety Information

The Investigator must promptly report to his or her IRB/EC all unanticipated problems involving risks to patients. This includes death from any cause and all SAEs reasonably or possibly associated with the use of ATYR1940 according to the IRB/EC's procedures.

The Sponsor will assess the severity and frequency of adverse drug reactions in adults versus pediatric patients, and will submit findings annually in the Development Safety Update Report/Annual Report.

8.5.10.7. Protocol Deviations Due to an Emergency or Adverse Event

Departures from the protocol will be determined as allowable on a case-by-case basis and only in the event of an emergency. The Investigator or other physician in attendance in such an emergency must contact the Medical Monitor as soon as possible to discuss the circumstances of the emergency.

The Medical Monitor, in conjunction with the Investigator, will decide whether the patient should continue to participate in the study. All protocol deviations and reasons for such deviations must be noted in the eCRF.

8.5.10.8. Pregnancy

Pregnancies occurring while the patient is receiving ATYR1940 or within 30 days after the patient's last dose of ATYR1940 will not be considered serious, but are to be reported using the same procedures as for SAEs described in Section 8.5.10.4.

ATYR1940 must be discontinued immediately in the event of a pregnancy. The patient should be referred to an obstetrician/gynecologist experienced in reproductive toxicity for further evaluation and counseling.

The Investigator will follow the patient until completion of the pregnancy, and must notify the Medical Monitor of the outcome within 5 days. The Investigator will provide this information as a follow-up to the initial report.

If the outcome of the pregnancy meets the criteria for immediate classification as an SAE (i.e., spontaneous abortion [any congenital anomaly detected in an aborted fetus is to be documented], stillbirth, neonatal death, or congenital anomaly), then the Investigator should report it as such. Furthermore, all neonatal deaths that occur within 30 days of birth are to be reported, without regard to causality, as SAEs. In addition, any infant death after 30 days that the Investigator suspects is related to the in utero exposure to the ATYR1940 should also be reported.

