Informed consent/assent	X ¹								
Confirm inclusion/exclusion criteria	X ¹								
Weight ⁵	X				X		X	X	
Vital signs ⁶	X ³	X					X	X	X
Complete physical examination	X			X				X	
Surveillance skeletal muscle MRI	X				X ⁷				X
ATYR1940 administration ⁸	X ¹	X							
12-lead ECG ⁹	X ³		X				X	X	
Pulse oximetry ¹⁰	X ¹	X					X	X	X
Pulmonary function tests ¹¹									
FEV ₁ , FVC, and FEV ₁ /FVC ratio	X ¹			X				X	
Total lung capacity and DLCO	X ¹				X			X	
Adverse events	X ³	X					X	X	X
Prior/concomitant medications	X ³	X					X	X	X
Manual muscle testing	X				X		X		

Assessment	Study Period / Frequency of Assessments								
	Treatment Period						Follow-up		
	Week 14 in Parent Study/ Week 1 in Current Study ^{1,2,3}	Weekly (W2, W3, etc)	Monthly (Q4W) (Week 4, 8, etc)	Every 6 weeks (Q6W) (Week 6, 12, etc)	Every 3 Months (Q12W) (Week 12, 24, etc)	Every 6 Months (Q24W) (Week 24, 48, etc.)	1-week F/U	4-week F/U	12-week F/U
Visit Window (days)	-	±3D ⁴	±3D ⁴	±3D ⁴	±5D ⁴	±5D ⁴	±3D	±3D	±5D
Upper and lower extremity function ¹²	X				X		X		
INQoL	X				X		X		X
FSHD-HI ¹³	X ¹				X		X		X
Laboratory Assessments									
Pregnancy test ¹⁴	X ³		X					X	
Hematology, serum chemistries, and urine analysis with microscopy ¹⁵	X		X				X	X	X
Plasma complement factors ¹⁶	X ¹				X		X		
Serum complement and tryptase levels ¹⁷	X ¹				X		X		
Jo-1 antibodies ¹⁸	X	X					X	X	X
ADA ¹⁹	X			X			X	X	X
HARS (human histidyl-tRNA synthetase; serum)	X							X	
Serum ATYR1940 concentrations ²⁰	X			X			X		
Muscle biomarkers	X ¹				X		X	X	
Biomarkers in blood	X				X		X	X	

Assessment	Study Period / Frequency of Assessments								
	Treatment Period						Follow-up		
	Week 14 in Parent Study/ Week 1 in Current Study ^{1,2,3}	Weekly (W2, W3, etc)	Monthly (Q4W) (Week 4, 8, etc)	Every 6 weeks (Q6W) (Week 6, 12, etc)	Every 3 Months (Q12W) (Week 12, 24, etc)	Every 6 Months (Q24W) (Week 24, 48, etc.	1-week F/U	4-week F/U	12-week F/U
Visit Window (days)	-	±3D ⁴	±3D ⁴	±3D ⁴	±5D ⁴	±5D ⁴	±3D	±3D	±5D
PBMCs for immunophenotyping (general and disease-related) and culture for immune protein release	X				X		X	X	
Assessments for Patients in Parent Study ATYR1940-C-003 Only									
Visual acuity	X ¹					X	X		X
Pure Tone Audiometry	X ¹					X	X		X

Note: On ATYR1940 administration days, laboratory samples are to be collected and assessments performed pre-infusion, unless otherwise specified.

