5.2. Exclusion Criteria

Patients meeting any of the following criteria are not eligible for study entry:

1. At any time during participation in the parent study, met a ATYR1940 discontinuation criterion, including, but not limited to:
 - a. Jo-1 Ab levels ≥ 1.5 U/mL.
 - b. Clinical evidence of a generalized IRR (see Section 7.5.5.1).
 - c. Clinical evidence of a National Cancer Institute (NCI) Common Terminology Criteria for Adverse Events (CTCAE) (version 4.03) \geq Grade 2, study-drug-related SAE.
 - d. Pregnancy.
 - e. Progression of disease that, in the opinion of the Investigator, precluded further participation in the study.
 - f. Withdrawal of consent or assent.
 - g. Other findings that, at the discretion of the Investigator and/or Sponsor, indicated that study drug administration should be discontinued.
2. Is expected to require treatment with curcumin or systemic albuterol (intermittent inhaled albuterol is permissible) during study participation; or use of a product

that putatively enhances muscle growth (e.g., insulin-like growth factor, growth hormone) or activity (e.g., Coenzyme Q, Coenzyme A, creatine, L-carnitine) on a chronic basis; or statin treatment initiation or significant adjustment to statin regimen (stable, chronic statin use is permissible).

3. Planned to receive any vaccination during study participation.
4. Abnormal baseline findings, medical condition(s), or laboratory findings that, in the Investigator's opinion, might jeopardize the patient's safety or decrease the chance of obtaining satisfactory data needed to achieve the objectives of the study.
5. Evidence of clinically significant cardiovascular, pulmonary, hepatic, renal, hematological, metabolic, dermatological, or gastrointestinal disease, or has a condition that requires immediate surgical intervention or other treatment or may not allow safe participation.
6. If female and of childbearing potential (premenopausal and not surgically sterile), has a positive pregnancy test at entry or is unwilling to use contraception from the time of entry through the 3-month Follow-up visit. Acceptable methods of birth control include abstinence, barrier methods, hormones, or intra-uterine device.
7. If male, is unwilling to use a condom plus spermicide during sexual intercourse from the time of entry through the 1-month Follow-up visit.

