6.2. Patient Management

All patients must provide written informed consent or assent, as appropriate, based on local age of majority, before the performance of any study-related procedures. Patients who are determined to be eligible for the study will be enrolled into the study at the baseline visit (Week 1) and will receive IV infusions of ATYR1940 weekly. Patients will attend posttreatment follow-up visits 1, 4, and 12 weeks following completion of dosing. The 12-week follow-up visit is the End-of-Study (EOS) visit.

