8.5.10.2. Adverse Event Assessment

All AEs will be collected and recorded in this study from the time of the first ATYR1940 dose in this study through the EOS visit, or after the end of the study, if thought to be related to study drug. (AEs occurring through 30 days after the last study drug dose in the parent study and those occurring >30 days after the last study drug dose in the parent study that are considered by the Investigator to be study drug-related are to be reported in the parent study.) This includes AEs the patient reports spontaneously, those observed by the Investigator, and those elicited by the Investigator in response to open-ended questions during scheduled study center visits. Furthermore, all AEs that presented in the parent study that are ongoing at Week 1 in the current study will be recorded as such.

Each AE is to be assessed by the Investigator with regard to the following categories.

Serious/Non-Serious

AEs that meet the criteria specified in Section [8.5.10.1.3](#) are to be considered serious.

Relationship to Study Drug

The relationship of each AE to ATYR1940 is to be assessed by the Investigator according to categories in [Table 8](#).

Table 8: Criteria for Determination of Adverse Event Relationship to Study Drug

AE (is):	Relationship between ATYR1940 and AE:				
	Category				
	None	Unlikely	Possibly	Likely	Definitely
Clearly the result of an external factor	Yes	No	No	No	No
Probably/possibly the result of another factor	No	Yes	Yes	No	No
Has a chronological relationship with the time of administration and/or represents a known reaction to Study Drug	No	No	Yes	Yes	Yes
Disappears or decreases after discontinuation of the Study Drug	NA	NA	NA	Yes	Yes
Recurr on renewed administration (re-challenge)	No	No	NA	NA	Yes or NA**

** A re-challenge is not required; if done, re-challenge would be expected to be positive.

NA Not applicable

Intensity

The intensity of each AE is to be assessed by the Investigator according to the NCI CTCAE, version 4.03. If the AE is not included in the NCI CTCAE, version 4.03, then the Investigator is to determine the intensity of the AE according to the following criteria:

- Mild (Grade 1): Asymptomatic or mild symptoms: clinical or diagnostic observations only; intervention not indicated.
- Moderate (Grade 2): Minimal, local, or non-invasive intervention indicated; limiting age-appropriate instrumental activities of daily living.

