8.5.10.4. Reporting Serious Adverse Events

SAEs will be collected and recorded throughout the study period, beginning with the signing of the ICF through the EOS visit, or after the end of the study if thought to be related to ATYR1940.

The Investigator must report all SAEs within 24 hours of discovery to:

[REDACTED]
Email: [REDACTED]
Telephone number: [REDACTED]

A completed SAE report is to be sent to the Medical Monitor's attention within 24 hours of discovering the event. The initial report should include at least the following information:

- Patient's ID number;
- Description and date of the event;
- Criterion for serious; and
- Preliminary assignment of causality to ATYR1940.

The Medical Monitor will contact the Investigator via telephone for follow-up information regarding the SAE, as appropriate.

The Investigator, or designated party, should notify the appropriate IRB/EC of SAEs occurring at the study center and other AE reports received from aTyr, in accordance with local procedures and statutes.

SAEs that are considered as possible or probably related to the investigational product, and as unexpected (i.e., SUSARs), will be reported to the concerned Competent Authorities (CAs) and IRBs/ECs by the Sponsor or Sponsor's designee as required by applicable local regulations. Per regulation, any fatal or life-threatening SUSAR will be reported to the CAs/IRBs/ECs within 7 calendar days, and additional information within an additional 8 calendar days. The Sponsor or Sponsor's designee is required to submit any other SUSAR to the CAs/IRBs/ECs within 15 calendar days of notification. The Sponsor or its designee is also responsible for notifying the investigational sites of all expedited SAEs. The Investigator must keep copies of all expedited SAE information including correspondence with the Sponsor on file.

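### Pregnancy reporting stops 30 days after the last dose and testing at the 4-week visit, although women are asked to use contraception to week 12

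*Protocol*

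**What the plan says.** **Contraception.** Under Protocol Section 5.2, criterion 6, a woman of childbearing potential is excluded if she "is unwilling to use contraception from the time of entry through the 3-month Follow-up visit". Section 6.2 sets follow-up visits at 1, 4 and 12 weeks after dosing ends and adds: "The 12-week follow-up visit is the End-of-Study (EOS) visit". No other visit fits the 3-month label.

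**Reporting.** Section 8.5.10.8 sends through the SAE procedure "Pregnancies occurring while the patient is receiving ATYR1940 or within 30 days after" the last dose. The investigator then follows the patient to the end of the pregnancy and notifies the outcome: "The Investigator will provide this information as a follow-up to the initial report". Spontaneous abortion, stillbirth, neonatal death and congenital anomaly are to be reported as SAEs. The section also says that "all neonatal deaths that occur within 30 days of birth are to be reported, without regard to causality, as SAEs".

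**Testing.** The "Pregnancy test" row of Table 1 is marked at Week 1, monthly during treatment, and at the 4-week follow-up. The 1-week and 12-week follow-up cells are blank. The copy of the table in SAP Section 3.1 is the same, and Protocol Section 8.2 refers back to Table 1 for on-study testing.

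**Other safety collection.** Section 8.5.10.2 collects AEs "from the time of the first ATYR1940 dose in this study through the EOS visit", or later if thought related to study drug. Section 8.5.10.4 says: "SAEs will be collected and recorded throughout the study period, beginning with the signing of the ICF through the EOS visit", again with later events included if thought related.

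**The concern.** The protocol sets a period in which women should avoid pregnancy, but a failure of that precaution in the second and third months after dosing triggers neither a test nor a pregnancy report. AEs and SAEs run to the 12-week visit, so pregnancy is the one safety item cut short.

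What is at stake is completeness of pregnancy follow-up. Outcome notification in Section 8.5.10.8 is framed as a supplement to an initial report. The SAE provisions for adverse pregnancy outcomes work only if the site knows that the pregnancy exists. For a conception after day 30, any delivery falls after End of Study, when SAE collection continues only for events thought related to the drug. A normal outcome might then never be recorded.

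**Working it through.** The plan gives no figure to reproduce, so the check is day arithmetic, with day 0 the last dose.

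**Inputs from the documents**
- 4-week visit: day 28, window ±3 days, so days 25 to 31 (Table 1).
- 12-week visit: day 84, window ±5 days, so days 79 to 89 (Table 1).
- Pregnancy reporting limit: day 30 (Section 8.5.10.8).
- Enrolment: up to 24 patients (Section 9.1), both sexes, aged 16 to 75 (SAP Section 1.1).
- Terminal half-life: about 3 to 6 hours (Section 2.3, healthy-volunteer study).

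**Length of the gap**
- Nominal: 84 − 30 = 54 days, which is 54/84 = 64% of follow-up.
- With the visit window: 79 − 30 = 49 to 89 − 30 = 59 days.

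**Expected pregnancies in the gap.** Assumption, not in the documents: 2 to 10% pregnancies per year under contraception.
- Upper bound, all 24 patients women of childbearing potential: 24 × 54 = 1,296 woman-days; 1,296/365.25 = 3.55 woman-years. Expected: 3.55 × 0.02 = 0.07 to 3.55 × 0.10 = 0.35 (from unrounded woman-years).
- If 12 are: 1.77 woman-years, giving 0.04 to 0.18.

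**Drug remaining at day 30.** 30 × 24 = 720 hours; 720/6 = 120 to 720/3 = 240 half-lives. Exposure is negligible.

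**What a test can see.** Assumption, not in the documents: a urine test turns positive 10 to 14 days after conception.
- Test on day 28: detects conceptions up to day 28 − 14 = 14 to 28 − 10 = 18. The last 30 − 18 = 12 to 30 − 14 = 16 days of the present reporting window are beyond its reach.
- Test on day 84: detects conceptions up to day 84 − 14 = 70 to 84 − 10 = 74. It covers the whole present window, but misses the last 10 to 14 days before the 12-week visit.

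**Early withdrawals.** Under Section 6.4.2 a patient leaving the study has the 1- and 4-week assessments within 7 days of the last dose, if feasible. Her last pregnancy test may fall then, and she may never attend week 12. The current 30-day limit, counted from the dose, still applies to her. A limit tied only to the 12-week visit might not.

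**The case against.** The two periods need not match. Contraception can carry a safety margin, while pregnancy reporting aims at possible drug exposure, and by day 30 at least 120 half-lives have passed. Criterion 7 in Section 5.2 also ends the male contraception requirement at the 1-month follow-up, so about a month is a horizon used elsewhere in the protocol. This stands: the mismatch is a design choice with a small cost, and nothing in the documents forbids it. But the sponsor did set the longer period for women, and no reason is given for reporting to stop sooner.

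A reader might infer that a pregnancy after day 30 would go unnoticed, or would come to light only if the patient volunteered it. The documents do not support that. At the 12-week visit Table 1 schedules adverse events and concomitant medications. Section 8.5.10.2 includes events elicited by open-ended questions, and Section 7.7 requires all medications, including vitamins, to be recorded. A miscarriage before End of Study falls within the SAE period. Pregnancy is not named in these checks, so they are possible routes to discovery and not a substitute for a reporting duty.

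The limited reach of the week-4 test is a weak argument by itself. A pregnancy conceived by day 30 stays reportable whenever it is found, the detection lag is assumed, and a week-12 test leaves a similar tail.

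**Conclusion.** The mismatch is real and worth a cheap improvement. For about 54 days in which women are asked to avoid pregnancy, the protocol schedules no test and sets no duty to report a pregnancy as such. The length rests on the documents alone, once the 3-month visit is read as the 12-week one. The expected count, at most about 0.35 pregnancies, rests on the assumed 2 to 10% annual rate and on treating every patient as a woman of childbearing potential.

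A reader might take the 12-week contraception rule as a sign that the sponsor expects fetal risk that late, or conclude that the safety results are compromised. Neither follows. The documents state no such risk, exposure is negligible by day 30, and SAP Section 9.6.2 only lists pregnancy test results. No conclusion of the study is expected to change.

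**What to change.** **Main change.** In Section 8.5.10.8, replace the 30-day limit with 12 weeks (84 days) after the last ATYR1940 dose, or the 12-week follow-up visit if that is later. Counting from the dose keeps a fixed window for patients who withdraw under Section 6.4.2.

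**Optional change.** In Table 1, add a urine pregnancy test for women of childbearing potential at the existing 12-week visit. Patients who only stop dosing are already asked to attend it (Section 6.4.1). The test will not detect conceptions just before that visit and will not reach early withdrawals.

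**Cost.** A minor amendment with IRB/EC approval (Section 10.4), and re-signing by active patients if the consent form is revised (Section 10.2); it could be bundled with another amendment. The optional test adds at most 24 urine tests in total. There would be slight extra reporting and follow-up of pregnancies with negligible drug exposure.

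**Timing.** The PK/PD analysis plan (Section 3.1) describes study conduct in the past tense. If follow-up has ended, the change can serve only later protocols.

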9. STATISTICAL ANALYSES

9.1. Statistical Basis for Sample Size

No formal sample size calculation was performed; patients that participated in the parent study and meet the entry criteria for the current study may be enrolled. Based on the design of the parent studies, it is estimated that up to 24 patients will be enrolled in this study.

9.2. Statistical and Analytical Plan

An overview of the statistical methodology to be employed is provided in the following subsections. Details regarding the statistical methodology will be documented in a formal Statistical Analysis Plan (SAP) prior to database lock. The methodology for serum ATYR1940 concentrations and PD analyses will be documented in separate SAPs.

9.2.1. General Methods

Statistical analyses will be primarily descriptive in nature, since the goal of the study is to determine the safety, tolerability, and immunogenicity of ATYR1940. This goal will be achieved by the results of a deterministic algorithm; thus, statistical hypothesis testing is neither intended nor appropriate within this context.

Continuous variables will be summarized using descriptive statistics (n, mean, standard deviation, median, minimum, and maximum). Categorical variables will be summarized showing the number and percentage (n, %) of patients within each classification.

Data obtained from the parent study will be combined with data from the current study.

For patients assigned to ATYR1940 in the parent study, data obtained from the parent study will be combined with data from the current study.

For patients who received ATYR1940 ≤ 4 weeks previously in the parent study, baseline refers to the baseline in the parent study (i.e., the most recent assessment obtained before the first study drug dose.) For patients who received ATYR1940 > 4 weeks previously in the parent study, baseline refers to assessment obtained before the first ATYR1940 dose at Week 1 in the current study.

9.2.2. Analysis Populations

All patients who have received at least 1 dose (partial or full) of ATYR1940 and have a postinfusion safety observation will be included in safety analyses. Additional analysis populations will be defined in the SAP.

9.2.3. Missing, Unused, and Spurious Data

Analyses will be based on observed data only; no data will be imputed.

9.2.4. Disposition of Patients

The numbers and proportions of patients who are enrolled in and complete the study and who are early terminations will be summarized. Reasons for study discontinuation after the start of study treatment will be tabulated.

9.2.5. Demographics and Baseline Characteristics

A summarization of demographic and baseline disease characteristic data, as documented in each parent study, will be presented for patients in this extension study. Data to be tabulated will include at least demographic and baseline characteristics such as sex, age, race, height, weight, and body mass index, and disease-specific diagnostic and historical information. Medical history also will be similarly summarized.

9.2.6. Extent of Exposure

Descriptive statistics will be presented overall and, if applicable, each dose level, for the number of doses received, percent of expected dose received, and actual dose received overall (i.e., across the parent and extension study), and in each the parent and extension study. Furthermore, descriptive statistics for the number of doses missed or held will be presented, if warranted by the data. A tabular summary and listing of drug administration and dose intensity and a by-patient listing of the date and time of each ATYR1940 dose and the dose administered also will be presented.

9.2.7. Prior and Concomitant Medications

Tabulations of prior and concomitant medications, coded using the World Health Organization drug dictionary, will be produced. All prior and concomitant medications administered will be presented in a data listing.

